### 4.3 Exploratory endpoints

Exploratory efficacy endpoints include the following:

- Assessment of Global Symptom Relief at Weeks 4, 12, and 24 as measured by patient, caregiver, and clinician via the global impression of change (GIC) item
- Change from baseline in fasting s-BA at Week 4
- Change in pruritus, as indexed by caregiver-reported observed scratching, from baseline by each 4-week interval of the Treatment Period as measured by the Albireo ObsRO instrument
- Change from baseline by each 4-week interval of the Treatment Period in patient-reported and observer-reported night time itching and scratching severity scores, respectively, as measured by the Albireo PRO and ObsRO instruments.
- Change from baseline by each 4-week interval of the Treatment Period in patient-reported and observer-reported morning time itching and scratching severity scores, respectively, as measured by the Albireo PRO and ObsRO instruments.
- Change from baseline by each 4-week interval of the Treatment Period in pooled pruritus score including observer-reported scratching for patients  $< 8$  years of age and patient-reported itch severity for patients  $\geq 8$  years of age, as measured by the Albireo PRO and ObsRO instruments, respectively.
- Change from baseline by each 4-week interval of the Treatment Period in additional patient-reported and observer-reported sleep parameters (e.g. tiredness and number of awakenings), as measured by the Albireo PRO and ObsRO instruments, respectively.
- Change from baseline to Week 24 in PedsQL
- Change from baseline in serum ALT concentration at Week 4

- Change from baseline in total bilirubin at Weeks 4, 12, and 24
- Change from baseline in AST and gamma-glutamyl transferase at Weeks 4, 12, and 24
- Change from baseline for other biochemical markers and measures of bile acid synthesis (autotaxin, plasma 7 $\alpha$ -hydroxy-4-cholesten-3-one concentration [p-C4]) at Week 24
- Change in paediatric end-stage liver disease/model for end-stage liver disease (PELD/MELD) score, AST to platelet ratio index (APRI) score, and Fib-4 score from baseline to Week 24
- Change from baseline to Week 24 in stage of liver fibrosis as assessed by Fibroscan® (where available)
- For patients who answered Yes to Questions 1 and 2 in the exit survey, changes from baseline in the average scratching score based on the Albireo ObsRO instrument in the last 2 weeks before treatment termination
- For patients who answered No to Questions 1 or 2 in the exit survey, changes from baseline in the average scratching score based on the Albireo ObsRO instrument in the last 2 weeks before treatment termination

#### 4.4 Safety

Safety criteria are as follows:

- Primary safety analysis is the incidence of treatment-emergent adverse events (TEAEs) and TEAEs categorized by causality, severity, and seriousness assessments made by the investigator by comparing active arms vs. placebo. This includes liver-related mortality and liver decompensation events ([protocol Section 10.2.2.3](#)) and all-cause mortality.
- Safety will also be evaluated by the following assessments:
  - Physical examinations
  - Concomitant medications
  - Vital signs
  - Laboratory test results (including clinical chemistry, hematology, urinalysis, AFP, vitamins A and E, 25-hydroxy vitamin D, and INR)
  - Abdominal ultrasound
  - Discontinuations due to AEs

## 5 SAMPLE SIZE AND POWER

For the EU and RoW, the primary analysis will be related to the serum bile acid responder endpoint. For the US, the primary analysis will be related to the pruritus endpoint. The CMH test stratified by randomization strata will be used to test the serum bile acid responder endpoint. The individual null hypothesis is that the odds ratio of the response in an active arm vs. placebo is 1. The alternative hypothesis is that the odds ratio is greater than 1. An ANCOVA will be used for treatment comparisons for the proportion of positive pruritus assessments at subject level. The individual null hypothesis is that the average proportion of positive assessments is the same between the active and placebo arms. The alternative hypothesis is that the average proportion is larger in the active arm.

Since each active arm will be compared with the placebo, there will be two individual null hypotheses for each endpoint. In each endpoint, a pooled analysis for the closed testing procedure will be applied to control the 1-sided overall type I error rate for the two odevixibat treatment comparisons vs. placebo at the 0.025 level [6,7,8]. The significance of an active arm will be claimed if both 1-sided p-values in the pooled analysis and individual treatment comparison are less than or equal to 0.025.

The study will enroll 60 to 70 patients in order to obtain at least 20 evaluable patients in each arm. For each primary endpoint, simulations with 5,000 iterations using 20 patients per arm were conducted to estimate the power after multiplicity adjustment, resulting in a standard error (SE) of <0.7% for each estimated power.

Based on the Phase 2 study (A4250-003) data, both low and high dose groups are assumed to have the same positive treatment effects in both the serum bile acid and pruritus endpoints in the simulation. For serum bile acids, binomial distributions were used to simulate the proportion of responders to estimate the power. The simulated proportions were analyzed using the Cochran-Mantel-Haenszel (CMH) test to generate the following 1-sided p-values: both odevixibat arms pooled vs. placebo, low dose vs. placebo, and high dose vs. placebo. Assuming 60% responders in the odevixibat arms and 10% responders in the placebo arm, the power to claim significance for a particular odevixibat arm after multiplicity adjustment is approximately 94%. The probability to claim significance for at least one arm, and for both arms are approximately 99% and 91%, respectively. If the response rates are 50% in the odevixibat arms and 10% in the placebo arm, with 20 patients per arm, the probability to claim significance for a particular odevixibat arm after multiplicity adjustment is approximately 82%. The probability to claim significance for at least one arm, and for both arms is approximately 91% and 73%, respectively.

For the proportion of positive pruritus assessments at the subject level in pruritus scores, beta-binomial distributions were used for power simulations since the binary results of the individual assessments within a subject are likely correlated [9]. The effect size was 1.0526 from the original sample size calculation using change from baseline as the endpoint. The same effect size was assumed for the current endpoint for the low and high dose vs. the control. A difference of 15%, 20%, 25%, and 30% in proportion of positive pruritus assessments were considered in power simulation. Within each difference, proportions of positive assessments in the placebo arm ranging from 15% to 35% were considered. Subsequently, the proportion of positive

assessments in an active arm, the standard deviation, and the corresponding beta binomial parameters were calculated to satisfy the assumed effect size. These parameters were used to simulate correlated binary results within each subject. The simulated proportions were analyzed using analysis of variance (ANOVA) to generate the following 1-sided p-values: both odevixibat arms pooled vs. placebo, low dose vs. placebo, and high dose vs. placebo. The simulation in each scenario was repeated for 5,000 iterations using the current sample size of 20 patients per arm. The simulated power to claim significance for a particular arm after multiplicity adjustment is quite consistent under different scenarios and is approximately 89%. The probability to claim significance for at least one arm, and for both arms is approximately 95% and 83%, respectively.

## 6 ANALYSIS SETS

### 6.1 Full Analysis Set (FAS)

The full analysis set (FAS) will consist of all randomized patients who received at least 1 dose of study treatment. Patients will be analyzed in the treatment group they were randomized to even if they received incorrect study drug. The FAS will be the primary analysis set for efficacy analyses.

### 6.2 Safety Analysis Set (SAS)

The safety analysis set will consist of all randomized patients who received at least 1 dose of study drug. Patients will be analyzed according to the treatment they actually received. In case of wrong study drug dispensed to a patient in error, the patient will be assigned to the treatment arm that the actual drug was mostly taken. The safety analysis set will be used for safety analyses.

### 6.3 Per-Protocol Analysis Set (PP)

The per protocol (PP) analysis set is a subset of the FAS and will consist of all randomized patients for whom no important protocol deviation (no deviation which may affect the study efficacy outcome) is documented. In identifying this population, important protocol deviations are defined as:

- Failure to meet the following inclusion criteria
  - Inclusion criteria (2) Patient must have a clinical genetic confirmation of PFIC-1 or PFIC-2 through identification of biallelic pathogenic variants in either the *ATP8B1* or *ABCB11* genes
  - Inclusion criteria (3) Patient must have elevated s-BA concentration, specifically measured to be  $\geq 100$   $\mu\text{mol/L}$ , taken as the average of 2 samples at least 7 days apart (Visits 1 and 2) prior to randomization
  - Inclusion criteria (4) Patient must have history of significant pruritus and a caregiver-reported observed scratching in the eDiary average of  $\geq 2$  (on 0 to 4 scale) in the 2 weeks prior to randomization
- Enrollment in spite of meeting the following exclusion criteria
  - Exclusion criteria (1) Patient with pathologic variations of the *ABCB11* gene that predict complete absence of the BSEP protein
  - Exclusion criteria (15) Patient suffers from uncontrolled, recalcitrant pruritic condition other than PFIC. Examples include, but not limited to, refractory atopic dermatitis or other primary pruritic skin diseases
- Compliance rate of  $< 80\%$  with study drug administration estimated based on CRF data

Important protocol deviations will be also identified by study team during protocol deviation review. The PP analysis set will provide supportive data for the efficacy analyses of primary and selected secondary endpoints.

## 7 STATISTICAL CONSIDERATIONS AND ANALYSIS

### 7.1 Handling of missing data and/or invalid data and outliers

#### 7.1.1 Handling of Missing data for efficacy endpoints

##### 7.1.1.1 Pruritus Endpoint

In the primary analysis of the pruritus endpoint, all intermittently missing assessments will be classified as negative pruritus assessments (that is, not meeting the definition of a positive assessment as defined in Section 4.1). Similarly, all missing planned assessments after premature treatment discontinuation will be counted as negative pruritus assessments. All planned assessments after death or initiation of rescue treatments such as biliary diversion surgery or liver transplantation will be counted as negative pruritus assessments. Both on-treatment and off-treatment pruritus assessments up to Day 168 will be included for analysis.

In general, all 336 (=168 x 2) assessments planned over the 24-week treatment period will be included in the denominator of the endpoint definition. However, if the last pruritus assessment for a patient who completes treatment (i.e., completes Week 24 assessment) is reported prior to Day 168, then the denominator used for analysis will be (the last report day x 2). The last report day will be determined for ObsRO and PRO instruments separately.

For the analysis of the pruritus endpoint, an additional method will also be used to calculate the proportion of positive pruritus assessments up to the last report day before or on Day 168. In other words, the denominator to calculate the proportion will be (the last report day x 2). All missing data before or on the last report day will be considered as negative assessments.

In addition, a multiple imputation method will be performed for pruritus assessments as a continuous endpoint by considering the impact of intermittently missing data as well as intercurrent events (Protocol Section 11.2.2.2). Moreover, a tipping point analysis will be performed to further evaluate the influence of missing data. The details of this are addressed in the Section 8.6.3.1.

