### **US primary endpoint**

- An additional method is used to calculate the proportion of positive pruritus assessments up to the last report day before or on Day 168. In other words, the denominator to calculate the proportion will be (the last report day x 2). All missing data before or on the last report day will be considered as negative assessments. This estimated proportion of positive pruritus assessments at the patient level over the 24-week treatment period based on the Albireo ObsRO instrument will be analyzed using the same approach as for the primary analysis.
- To address the concern that results from subjects with a baseline AM or baseline PM average score less than 2 may be difficult to interpret, additional supportive analysis will exclude patients from the primary endpoint analysis who have a baseline AM or baseline PM average score that rounded to 0 or 1.
- A supportive analysis of pruritus assessments as a continuous endpoint will be conducted. The analysis will be performed by considering the impact of intermittently missing data as well as intercurrent events.

The monthly (28-day) average in change from baseline for AM and PM, respectively will be calculated. There is a total of 6 monthly averages for AM assessments and 6 monthly averages for PM assessments over the 24-week treatment period. A mixed-effect model for repeated measures (MMRM) will be used to compare treatment effects at the last 28 days for AM and PM, respectively. Since missing not at random (MNAR) may occur, missing monthly average will be imputed with data from control arm completers using multiple imputation (MI). If there are subjects in the active arms who discontinued the study due to, e.g., relocation, their missing values may be imputed using active arm completers. To simplify the MI procedure, the description below only pertains to imputation using placebo completers. The MMRM model will include baseline score, treatment group, time (in month), treatment-by-baseline interaction, treatment-by-time interaction and stratification factors (i.e., PFIC type and age category). Unstructured covariance matrix will be used.

The following procedures in MI will be followed:

1. Intermediate missing values are imputed by the Markov Chain Monte Carlo (MCMC) imputation model, so only monotone missing values exist after imputation. 200 imputed data

sets will be created.

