	
Rounded baseline score will be used for the primary analysis. Additional analysis will be conducted based on unrounded baseline score.
 
In general, all 336 assessments planned over the 24-week treatment period will be included in the denominator of the endpoint definition. However, if a completer's last pruritus assessment is reported prior to Day 168, then (the last report day x 2) will be used as the denominator. The last report day will be determined for ObsRO and PRO instruments separately.
 
Regarding the proportion of positive pruritus assessments for each 4-week interval, the proportion is calculated up to the last interval with at least 50% of planned assessments.

Derivations for Safety Parameters	
Adverse Events (AE) duration (days)	AE end date – AE start date +1
Treatment Emergent Adverse Event (TEAE)	An AE (classified by preferred term) that occurs during the Treatment Period will be considered a TEAE if it has a start date on or after the first dose date of study drug, or it has a start date before the date of the first dose date of study drug, but worsened in severity on or after the date of the first dose date of study drug.

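### For treatment completers the US primary denominator stops at the last diary report with no lower limit, so missing entries after it are dropped, and no planned analysis of the proportion tests this

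*SAP*

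**What the plan says.** Section 7.1.1.1 gives the general rule: "In general, all 336 (=168 x 2) assessments planned over the 24-week treatment period will be included in the denominator of the endpoint definition". Two missing-data rules go with it. Within the diary record, "all intermittently missing assessments will be classified as negative pruritus assessments". After stopping treatment early, "all missing planned assessments after premature treatment discontinuation will be counted as negative pruritus assessments".

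An exception covers anyone who reaches the Week 24 assessment with a final diary report earlier than Day 168. In that case, "then the denominator used for analysis will be (the last report day x 2"). Appendix A has the same exception: "then (the last report day x 2) will be used as the denominator". Neither place sets a minimum last report day or a minimum number of entries. According to the revision history, the exception came in with version 1.1.

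Sections 7.1.1.1 and 8.6.3.1 add a second method that uses last report day x 2 for every patient. For that method, "All missing data before or on the last report day will be considered as negative assessments".

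**The concern.** The endpoint is described as covering the 24-week treatment period, with missing data counted against the patient. The exception reverses this for one kind of missing data, a completer's terminal gap. A gap is negative if any later entry exists and is ignored if none does.

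An allowance for an early Week 24 visit is reasonable, but the rule as drafted goes well beyond one. It is triggered by the last diary report, not by the visit, and applies equally to a diary that stops three days or twenty weeks early. Both completion and diary abandonment happen after randomisation. What is at stake is the meaning of the US primary endpoint and whether the reader can see how far the result depends on this choice.

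**Working it through.** **Inputs.** Planned denominator: 168 x 2 = 336 (Section 7.1.1.1, reproduced). Completer denominator: 2 x D, where D is the last report day (Section 7.1.1.1, Appendix A). Arm size 20 and planned differences of 15 to 30 points (Section 5). Visit 9 at Day 168 ±3 (Table 1). The positive rate while reporting, r, is an assumption; 70% is used below.

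**Formulas.** Score under the SAP rule = r x 2D / 2D = r. Score on 336 = r x 2D / 336 = r x D/168. Shift in a 20-patient arm mean per such patient = r x (1 - D/168) / 20.

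| D | Assessments dropped (336 - 2D) | SAP score | Score on 336 | Arm-mean shift, points |
|---|---|---|---|---|
| 28 | 280 | 70% | 11.7% | 2.9 |
| 84 | 168 | 70% | 35.0% | 1.75 |
| 126 | 84 | 70% | 52.5% | 0.88 |
| 154 | 28 | 70% | 64.2% | 0.29 |
| 165 | 6 | 70% | 68.75% | 0.06 |

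For Day 84: 0.70 x 168 = 117.6 positives; 117.6/168 = 70%; 117.6/336 = 35%; (70 - 35)/20 = 1.75. With r between 50% and 80% the Day-84 shift is 1.25 to 2.0 points and the Day-154 shift is 0.2 to 0.3.

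**Discontinuity.** Give the Day-84 stopper one more entry, on Day 168. The last report is then no longer before Day 168, so the denominator is 336. If the entry is negative, the score is 117.6/336 = 35%. If it is positive, the score is 118.6/336 = 35.3%. Reporting once more halves the score either way.

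**Is the visit window enough to explain the rule?** A visit three days early costs about 6 of 336 assessments (1.8%). This is approximate, because Table 1 counts from randomisation as Day 0 and Appendix A counts study days from first dose. The SAP foresees longer gaps: Section 8.6.4 deals with completers whose diary ends too early for a Week 24 bi-weekly or monthly score. In Appendix A a bi-weekly AM or PM score is missing once 8 of 14 entries are missing, which, absent other gaps, means stopping about eight days early.

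**Is there a floor elsewhere?** Section 9, item 2(k), refers to a 50% rule in Appendix A. For this proportion, Appendix A applies it only to the 4-week intervals, not to the 24-week figure.

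**Does a planned analysis test it?**
- The additional method truncates for every patient, so it is more lenient than the primary rule.
- The rank-based, unrounded-baseline, per-protocol and baseline-exclusion analyses leave the denominator alone.
- The MMRM with multiple imputation and tipping point (Section 8.6.3.1) does reach such completers, because its imputation group is anyone without an average in the last 4 weeks. It works on the continuous score, not the proportion.

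No analysis of the proportion keeps the full planned denominator for completers.

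**The case against.** The best defence has four parts.

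- **Completers and dropouts differ by design.** Premature discontinuation is an intercurrent event and completion is not, so different scores for identical diaries need not be a contradiction. This stands. The narrower inconsistency remains: within completers, intermittent gaps are negative and terminal gaps are dropped.
- **Long silence is unlikely.** Section 3.1 has the study nurse review the diary and call when both entries on a day are missing. This makes a Day-84 stop in a patient attending every visit improbable, but does not exclude it, and the SAP itself provides for diaries that end early.
- **The rule is the same in all arms.** A reader might infer that it favours odevixibat. The documents do not support that: the rule also raises placebo completers who stop early, and nothing in the SAP links diary abandonment to response or arm.
- **Missing data are tested.** A reader might infer that nothing examines this scenario. That is too strong, since the control-based imputation and tipping point do so on the continuous score.

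Two further inferences go beyond the text. The SAP nowhere says that an early Visit 9 is the only acceptable reason for a short diary. Nor does Section 8.6.4 state the denominator for the endpoint of positive assessments more than half the time, so a change there (70% passes, 35% fails) is plausible but not documented.

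**Conclusion.** The point holds as a drafting weakness in the US primary endpoint that should be fixed; it does not show that the result is biased. The exception has no lower limit and is tied to diary behaviour, so terminal missing entries of completers escape the missing-as-negative rule, and no planned analysis of the proportion shows the effect.

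The wording and the arithmetic are certain. The practical size is not. It depends on how many completers stopped early, when, and in which arm, none of which the SAP gives. As an illustration with 70% positive entries, three Day-84 stoppers, all in one arm of 20, would move its mean by 3 x 1.75 = 5.25 points, against planned differences of 15 to 30. Three Day-154 stoppers would move it by about 0.9 (3 x 0.29).

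**What to change.** In Section 7.1.1.1 and Appendix A, replace the last report day for completers by the Week 24 visit: count all assessments planned up to that visit, capped at 336, for example 2 x min(168, Visit 9 study day - 1), with every missing entry in that span negative.

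The subtraction of one day follows the diary windows in Appendix B, where the Day 1 AM entry belongs to baseline and the treatment span runs from Day 1 PM to Day 169 AM. A visit on study day V then allows 2 x (V - 1) entries up to that morning: 336 for V = 169 and 330 for V = 166. A completer with an early visit is not charged for entries that could not be made. The numerator should use the same span, and the Day 168 limit in the text should be worded to match.

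Keep last report day x 2 as the additional method already planned, and add one sensitivity analysis with 336 for every patient.

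The cost is a few sentences before database lock and one extra run, using a visit date already collected. The downside is slightly lower proportions for completers with incomplete diaries.
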